- Impact of Vision Impairment Questionnaire (4) and Independent Mobility Questionnaire (6)
- Mobility testing, as detailed in below (Aim 2)

Participants will be fit with HMD technology (Epson Moverio www.epson.com/moverio; **Figure 2**) and undergo a brief training with the investigators to learn about use of the device and will receive materials describing how to charge the device and turn it on and off. While wearing the device the subjects may have some discomfort related to the weight of the device on the ears and/or nose. The nose piece can be adjusted with pads for optimal comfort. A band on the arm pieces of the frame can also be adjusted for comfort. Initially, there may be the sense of disorientation, may feel dizzy or nausea, but with coaching/training the subject is anticipated to adapt. In order to adapt to the technology, participants will be permitted to bring the HMD home to use (for 2-4 weeks).

When participants return after a period of adaptation to the HMD, they will undergo the following:

- Impact of Vision Impairment Questionnaire (4), Independent Mobility Questionnaire (6), and the System Usability Scale (12)
- Videotaped open-ended interview in which subjects will be asked to describe their experience using HMD and to discuss any challenges and successes using the technology.
- Goldmann visual field and tablet visual field examination (while wearing the HMD)
- Mobility testing, as detailed below (Aim 2; while wearing the HMD)

To accomplish Aim 1 we will use the following approaches:

After the period of in-home adaptation, participants will return to have their visual field retested with Goldmann perimetry after a period of adaptation to the technology. We predict the outcome of increased planimetric area of the peripheral vision determined by Goldmann perimetry.

To accomplish Aim 2:

We propose to collect and analyze gait and head movement parameters in order to provide a quantitative analysis of mobility-associated factors of persons with severe visual field constriction and controls with and without the use of optical head-mounted display technology. We will mount an inertial measurement unit (IMU) data logger (Actigraph GT9X "Link", <http://www.actigraphcorp.com/products/actigraph-link/>; **Image 2**) on the patients' shoe; it will be placed inside a small pouch that rests on top of the shoe laces. A second IMU device will be mounted on

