the frames of the patients' existing glasses (or on a mock frame if the patient does not wear glasses) in order to measure head pitch, roll and yaw. The subjects will be asked to walk around a long empty corridor during which time they will be timed and videotaped and IMU data will be acquired. Then, participants will be asked to walk the same corridor after obstacles are arranged in the corridor every 1-2 meters. Obstacles will be short pieces of foam lying on the floor, knee to waist high cardboard boxes, or pieces of foam hanging from the ceiling. A research assistant will follow close to participants in order to provide assistance should this be required. Testing mobility in the presence of obstacles is important in order to more closely approximate real-world scenarios. Video recording is essential in order to correlate aberrancies in IMU data with obstacles in the patients' environment. The same procedure will be repeated with the patients wearing optical head-mounted display technology after the period of in-home adaptation to the technology with the device turned off (to serve as a negative control) and with the device turned on.

To accomplish Aim 3:

Participants will all complete the Impact of Vision Impairment and Independent Mobility Questionnaire at the time of their enrollment in the study. These surveys will be completed again after the period of in-home adaptation to the OHMD. We will also analyze qualitative data collected through open-ended interviews after use of HMD.

We will conduct statistical analyses, as detailed in Section 2e, to describe associations between outcomes assessed throughout our Aims.

b. Eligibility

Participants with retinal dystrophy will be recruited into this study from the Retinal Dystrophy Clinic in the Department of Ophthalmology and Visual Sciences at the University of Michigan.

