Secondary Outcome Measures:

- Change in gait speed compared to baseline (measured in seconds):
Gait speed will be measured using an inertial measurement unit attached to participants' shoes and will quantify the time taken to move from the beginning to end of a short mobility course.

Other Outcome Measures:

- Change in patient-reported ability for independent mobility as assessed by subject responses a validated questionnaire:
Independent Mobility Questionnaire (scored from 35 to 175 with 175 representing extreme mobility impairment)
- Change in patient-reported mobility and independence as assessed by subject responses a validated questionnaire:
Mobility and Independence domain of the Impact of Vision Impairment Questionnaire (scored from 0 to 33 with 0 representing poor mobility and independence)
- Change in stride length compared to baseline (measured in mm):

Inertial measurement units attached to participants' shoes will track the length of each step as they walk through a short mobility course.

- Change in stride width compared to baseline (measured in mm):
Inertial measurement units attached to participants' shoes will track the width of each step as they walk through a short mobility course.
- Change in foot orientation compared to baseline (measured in degrees):
Inertial measurement units attached to participants' shoes will track the orientation of their feet as they walk through a short mobility course.

e. Planned Data Analysis

To address Aim 1 the visual field will be assessed before and after being trained to use optical head-mounted display technology. The Goldmann visual field plots will be scanned and the planimetric areas for each stimulus size will be measured using Adobe Photoshop CC (San Jose, CA) as previously described (8). In brief, using a scale of 10 degrees on the visual field, the corresponding number of pixels are determined, and the units are set to millimeters. Areas are measured in mm² using the Magic Wand tool and are converted to degrees squared. Areas of scotomas are subtracted from the total area. We will analyze the change in area before and after a 2-4 week period of adaptation to the OHMD. The adaptation period is important as it will allow subjects to become familiar with how to use the device and to gain insight into how using such a device may impact their life. The Mann-Whitney U test will be used to compare change in visual field area between patients and controls.

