To address Aim 2 we will measure change in gait speed with and without the use of OHMD. We will calculate percent preferred walking speed to compare the ratio of gait speed measured in the presence and absence of physical obstacles. We will also use our data processing algorithms to reconstruct the paths of the feet and head movements during the planned experiments from which we can estimate mobility parameters (9–11). For gait, we will gather measures of stride length, width and period, and their variabilities, from straight-line walking, lateral/foot-angle relation, stride frequency, ground contact time, etc. For head movement we will gather measures of head pitch, head roll and head yaw. The mean and standard deviation of each gait and head movement parameter will be compared before and after being trained to use optical head-mounted display technology (11,12). We will use Wilcoxon signed-rank test to test for significant differences. Significant changes (and trends) will be assessed for direction and magnitude, and resulting values will be compared to gait and head movement parameter norms before and after using the optical head mounted display. The Mann-Whitney U test will be used to compare changes in gait parameters between patients and controls.

To address Aim 3 we will use the Wilcoxon signed-rank test to determine whether individual participants' survey scores changed from baseline when using optical head mounted display technology. We will also use the Mann Whitney U test to compare changes in survey scores between patients and controls. Cohen's d will be calculated to measure the overall effect size of the intervention as measured by the surveys. Minimum clinically important differences will also be calculated (ratio of change in visual ability to 1.95 standard errors of the measured change) to determine if changes in each individual's visual ability were clinically important.

We will also calculate Spearman correlations between variables (visual field area, mobility parameters and survey results) and use multiple regression to investigate associations while controlling for covariates.

Image 1. The Epson Moverio® Head Mounted Display.

Image 2. The Actigraph Link Inertial Motion Unit.

References

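### Does the stride-width outcome need a sensor on each shoe that the Aim 2 set-up does not provide?

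*Combined protocol and SAP*

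**What the plan says.** Three parts of the Methods bear on this.

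- **a. Study Design, Aim 2.** A single logger goes on the shoe, in these terms: "it will be placed inside a small pouch that rests on top of the shoe laces. A second IMU device will be mounted on". The site then named for that second unit is not the other shoe but spectacles: "the frames of the patients' existing glasses (or on a mock frame if the patient does not wear glasses". The purpose of the second unit is head pitch, roll and yaw. No unit on the other shoe is mentioned.
- **d. Outcome measures.** The secondary outcome uses the singular: "Gait speed will be measured using an inertial measurement unit attached to participants' shoes". The Other outcomes of stride length, stride width and foot orientation use the plural. For width the text is "Inertial measurement units attached to participants' shoes will track the width of each step as they walk through a short mobility course". The unit is mm; no formula, pair of feet or reference line is given.
- **e. Planned Data Analysis, Aim 2.** The team's algorithms, with cited method papers, will "reconstruct the paths of the feet and head movements during the planned experiments". For gait, "we will gather measures of stride length, width and period, and their variabilities, from straight-line walking". Then "The mean and standard deviation of each gait and head movement parameter will be compared before and after being trained", with Wilcoxon signed-rank tests within participants and Mann-Whitney tests on changes between patients and controls. Finally, "resulting values will be compared to gait and head movement parameter norms".

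**The concern.** Read literally, the set-up puts one sensor on one foot, while the outcome list and the analysis section speak of units, of every step and of both feet. An operator working from the set-up would fit one shoe unit; a reader of the outcome list would expect two.

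The difference matters for width in a way that it does not for stride length or timing. One foot's track shows where that foot lands relative to its own previous landing. It does not show where the other foot is. If stride width means the gap between the feet, a single shoe unit cannot give its mean. Any mean computed from same-foot landings would then be either about zero or a measure of how variable foot placement is.

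Because the analysis compares means as well as standard deviations, and then looks to norms, a change in variability could be reported as a change in gait width. A comparison with between-feet norms would also not be like for like. A baseline mean width missed at enrolment could not be recovered later.

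**Working it through.** The documents give no expected width, SD or effect size for this outcome, so there is no figure of the plan's to reproduce. The check has two parts: the geometry under assumed values, and then what the text requires.

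**1. One shoe unit, displacement between footfalls.** Assumed model, not from the documents: the lateral position of one foot at landing k is y_k = w/2 + e_k, where w is the distance between the feet and the e_k are independent N(0, s²). The stride-to-stride lateral displacement is d = y_(k+1) − y_k, so w/2 cancels and d ~ N(0, 2s²).

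- Signed mean: the differences telescope to (last position − first position)/number of strides. This is about 0 in straight-line walking, whatever the noise distribution.
- Absolute mean: 2s/√π = 1.128s.
- SD: √2·s = 1.414s.
- Ratio of absolute mean to SD: √(2/π) = 0.80. This ratio depends on normality; the cancelling of w does not.

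| Assumed s (mm) | Signed mean (mm) | Absolute mean (mm) | SD (mm) |
|---|---|---|---|
| 10 | 0 | 11.3 | 14.1 |
| 20 | 0 | 22.6 | 28.3 |
| 30 | 0 | 33.9 | 42.4 |

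These values are the same for w = 80, 120 and 200 mm. A separate simulation with w = 60, 100 and 140 mm and s = 15, 25 and 35 mm agrees: absolute means of about 16.9, 28.2 and 39.5 mm at every w.

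**2. Two shoe units.** With both feet located in one frame, the simulated mean recovers w. That needs more than a second logger. An assumed heading mismatch θ between the two tracks gives a lateral error of 1000·sin θ mm per metre walked: 8.7, 17.5 and 34.9 mm for 0.5, 1 and 2 degrees. If each track also starts from its own unrecorded origin, the mean is off by the starting separation.

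**3. What the text requires.** The geometry bites only if two things hold together: one shoe unit, and an intended between-feet width.

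| Reading | Consequence |
|---|---|
| Two units, between-feet width | Measurable once the tracks are aligned; the set-up sentence is loosely worded |
| One unit, lateral path excursion of that foot within a stride | Measurable; its mean need not be zero or tied to placement SD |
| One unit, displacement between footfalls | The SD is informative; the mean should not be called gait width |
| One unit, between-feet width | Not measurable |

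The sensor count cannot be settled from grammar. The gait-speed line pairs a singular unit with plural shoes, so the plural units in the width line may mean one per participant, counted across participants. Nor do the documents say that stride width is a between-feet distance. The analysis section places it beside stride length and period, a family that one foot can supply, and it reconstructs whole foot paths, not only landing points. The norms are not described as between-feet norms.

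**4. What is untouched under every reading.** Goldmann field area (primary), gait speed (secondary), same-foot stride length, stride timing, the orientation of the instrumented foot, and stride-width variability, which the analysis section already lists.

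**The case for a change.** The strongest case for a change is that a listed outcome should be identifiable from the protocol itself. Here the outcome has a unit and a phrase that mixes stride with step, and the set-up sentence, which is complete, accounts for both sensors without a second shoe. Whichever reading is right, something is loosely worded. If the one-unit reading is right, an analyst could tabulate a mean that says nothing about how far apart the feet are, and then correlate it with field area and survey scores. Rewording would cost almost nothing.

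Much of this stands as description. The sections do not match in wording, the protocol text gives no formula, and a mean of same-foot displacement between landings should not be presented as gait width.

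What does not stand is the step from loose wording to a flaw in the trial. The harm needs a particular combination of readings that the text does not establish. The calculation tests two definitions, signed and absolute displacement between landings, neither of which is the plan's, and it leaves out within-stride path excursion. The within-person tests and the comparison of changes use a quantity obtained by the same procedure at each visit, so they remain coherent for whichever definition the algorithms implement.

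The remedies gain little. Under one sensor, the substitute outcome is a variability that the analysis section already includes. Under two, the remedy adds hardware, synchronisation and alignment to serve one Other outcome.

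**Conclusion.** No change to the plan is called for. The mismatch over the number of shoe units and the absence of a stride-width formula are real, but they are missing detail of a kind that the team must settle before its reconstruction software produces any width value. Analysts who know which foot or feet were instrumented will know what their width variable is.

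The reach is small: one Other outcome in a pilot aiming for ten patients and ten age-matched controls with complete data. The primary and secondary outcomes do not depend on it. The figures of 11.3 to 33.9 mm for the absolute mean rest on assumed placement SDs and an assumed definition. They illustrate what one shoe unit cannot show; they do not demonstrate an error in this trial.

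The conclusion assumes that the reported width will be described as what was actually measured. The cited method papers were not available, so whether they define stride width is not judged here.

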Optical Head-Mounted Display Technology for Low Vision Rehabilitation

NCT02983305

June 15, 2018

PROTOCOL

1. Background

Worldwide it is estimated that 191 million people have moderate to severe visual impairment (MSVI) and an additional 32.4 million are blind (1). Patients with uncorrectable MSVI may undergo low vision rehabilitation (LVR), which has been shown to improve functional abilities, such as mobility (2). However, existing LVR strategies do not adequately address severe visual field constriction, and much of the evidence that points toward improved functional performance from LVR is based on patient self-report (3). Accordingly, there is a **critical barrier** to improving and measuring function among patients with severe visual field constriction that we seek to address.

In this pilot study, we will test the **hypothesis** that optical head-mounted display technology expands constricted visual fields and improves mobility and quality-of-life. While there are many causes and forms of visual impairment, our **objective** is to assess optical head-mounted display technology in LVR for patients with severely constricted visual fields resulting from retinal dystrophy.

Objectives/Specific Aims

We will test our hypothesis in the following aims:

Primary Aims

1. To demonstrate that optical head-mounted display technology increases the planimetric area of the visual field.

Other Aims

2. To quantify the impact of optical head mounted display technology on mobility using gait and head movement analyses.
3. To measure the impact of optical head mounted display technology on vision-related quality of life and self-reported function.

1. Methods

a. Study Design

Demographic data, medical history, laboratory results, medications and clinical information will be extracted from the medical record, including visual acuity and results of visual field, electroretinogram, ultrasound, optical coherence tomography, MRI and CT.

Participation in the study will occur on two separate days 2-4 weeks apart.

Upon enrollment all participants will complete:

- Measurement of height, weight and limb length
- Measurement of visual acuity and contrast sensitivity
- Full ophthalmologic examination including intraocular pressure measurement, slit lamp biomicroscopy and indirect ophthalmoscopy
- Goldmann visual field examination
- Windows tablet visual field examination
- Electroretinogram (if not done in year prior to enrollment; only done by patients, not controls)

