Normal controls will be included to adjust for the baseline impact of HMD on visual fields and gait parameters and to compare these to data from patients with RP. Comparing to a group of age-matched control patients will allow us to investigate and understand the true impact of HMD on visual fields, gait, and quality of life. Control participants will be recruited from the Comprehensive and Pediatric Ophthalmology Services at the University of Michigan. We will seek to enroll up to 40 subjects in order to obtain ten patients and ten age-matched controls with complete data, allowing room for those who don't complete both study visits and technical errors with equipment.

Criteria

Inclusion criteria for subjects with retinal dystrophy:

- diagnosis of retinal dystrophy
- severe vision loss that constitutes legal blindness
- able to perform a reliable Goldmann visual field test
- constricted visual field less than or equal to 20 degrees by Goldmann perimetry using the III4e stimulus in at least one eye with best-corrected visual acuity $\geq 20/60$

Inclusion criteria for control subjects:

- healthy controls
- able to perform a reliable Goldmann visual field test

Exclusion criteria for subjects with retinal dystrophy:

- movement disorder that precludes evaluation of mobility
- functional vision loss
- pregnant women

Exclusion criteria for control subjects:

- visually significant ocular condition other than correctable refractive error
- movement disorder that precludes evaluation of mobility
- functional vision loss
- pregnant women

c. Study Setting

Patients will be recruited from the Retinal Dystrophy Clinic of the Department of Ophthalmology and Visual Sciences at the University of Michigan; controls will be recruited from the Comprehensive and Pediatric Clinics of the Department of Ophthalmology and Visual Sciences at the University of Michigan. Study exams, clinical testing, surveys and interviews will be completed in the Kellogg Clinical Research Center. Mobility testing will be conducted in a hallway located in the Kellogg Clinical Research Center.

d. Outcome measures

Primary Outcome Measures:

- Change in the planimetric area of Goldmann visual field with the use of head-mounted display technology compared to baseline (measured in degrees squared):
Using computer software we will calculate the area of participants' Goldmann visual fields in order to obtain a summary quantitative measurement of the extent of peripheral vision.

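### Does Aim 1 need to name the stimulus, eye and monocular or binocular field behind its single visual field area?

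*Combined protocol and SAP*

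**What the plan says.** - Section d (Outcome measures) gives one primary outcome: "Change in the planimetric area of Goldmann visual field with the use of head-mounted display technology compared to baseline". Software is used to calculate the area "in order to obtain a summary quantitative measurement of the extent of peripheral vision".
- Section e (Planned Data Analysis, Aim 1) says that "the planimetric areas for each stimulus size will be measured using Adobe Photoshop CC". Scotoma areas are subtracted and the change over the adaptation period is analysed. The only test named for Aim 1 is: "The Mann-Whitney U test will be used to compare change in visual field area between patients and controls".
- Section b (Eligibility) contains the only named stimulus and the only mention of an eye. Patients need a "constricted visual field less than or equal to 20 degrees by Goldmann perimetry using the III4e stimulus in at least one eye", with an acuity condition on that eye. Controls have no corresponding eye rule.
- Section a (Study Design) lists a "Goldmann visual field examination" at enrolment, before the device is fitted, and "Goldmann visual field and tablet visual field examination (while wearing the HMD" at the return visit. It does not say whether fields are monocular or binocular. Device off and device on are distinguished only for the mobility course.

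**The concern.** Several areas per participant go in and one value has to come out, but the rule for getting from one to the other is not written down. III4e and the reference to an eye belong to patient entry, so they do not bind the analysis. The citation attached to the Photoshop method does not help either: the text summarised from it covers scaling, conversion to degrees squared and scotoma subtraction.

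If the stimulus or eye were picked after the data were seen, the apparent result for the only primary aim could depend on that pick. With ten per group, correlated isopters need not all fall on the same side of a significance threshold. A pilot outcome that is not fixed is also harder to carry into a later trial.

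**Working it through.** The plan states no significance level, power, effect size or standard deviation, so it has no figure of its own to reproduce. The calculations below only size the consequence.

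**Input from the plan.** Ten patients and ten controls with complete data (section b).

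**Assumptions not in the plan.** Two-sided 0.05; exact Mann-Whitney test; two or three candidate areas; normal changes with equal variance and equal correlation between areas.

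**1. Size of one test.** At 10 v 10 the exact test rejects if U ≤ 23 or U ≥ 77. Its attained size is 0.0433.

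**2. Chance of at least one false positive among k areas.** For uncorrelated areas this is 1 − (1 − 0.0433)^k:

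- k = 2: 1 − 0.9567² = 0.085
- k = 3: 1 − 0.9567³ = 0.124

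For correlated areas, simulation (40,000 trials per cell) gives:

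| Correlation | k = 2 | k = 3 |
|---|---|---|
| 0.5 | 0.080 | 0.113 |
| 0.8 | 0.070 | 0.090 |
| 0.9 | 0.062 | 0.078 |

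The areas come from the same field, so the lower rows are more plausible. There the excess over a single test is about 2 to 3 percentage points for two areas (0.062 or 0.070 less 0.043) and 3 to 5 for three (0.078 or 0.090 less 0.043).

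**3. Disagreement among three areas when an effect exists.** This is the share of trials in which some but not all of the three areas are significant, with the same true difference in each (20,000 trials per cell):

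| True difference | Correlation 0.9 | 0.8 | 0.5 |
|---|---|---|---|
| 0 SD | 6% | 8% | 11% |
| 0.5 SD | 15% | 21% | 31% |
| 1 SD | 26% | 35% | 53% |
| 1.5 SD | 15% | 19% | 29% |
| 2 SD | 3% | 4% | 5% |
| 3 SD | 0% | 0% | 0% |

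Repeat runs differ by about one percentage point. Of the differences tried, disagreement is greatest at 1 SD, where a single test has about 51% power. The plan gives no reason to expect that effect size rather than a larger or smaller one.

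**4. What the text already settles.** The viewing condition is less open than it looks. Section a has the return field done with the device worn, and section d contrasts use of the device with baseline. That contrast is the outcome, so the two visits are meant to differ in this respect. What stays unstated is the stimulus, the eye, monocular or binocular mode, and an explicit on or off state for the return field.

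**The case for a change.** The strongest argument for a change is that the plan does name a primary outcome and a between-group test, and that one or two sentences would pin the value down. Even at correlation 0.9, a 1 SD effect leaves about one trial in four with isopters that disagree. Pilot status is no excuse if the purpose is to hand an outcome on to a larger study.

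Much of this stands as description. III4e is an entry criterion, not an analysis rule, and controls have no eye rule. It falls short as a reason to change the plan on four counts.

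- Section e measures every stimulus size, which fits with reporting all of them. If all are reported, selection after the fact does not arise.
- The one-in-four figure holds at the least favourable effect size in the table and falls to 3% at 2 SD. Equal-variance normal changes are also doubtful when patients have fields of 20 degrees or less and controls have no significant eye condition.
- No formal decision hangs on the p-value. Aim 1 is that the device enlarges the field, whereas the Mann-Whitney test compares the change between groups, and no threshold for success is set.
- The choice among isopters, between a qualifying eye and a fixed eye, or of a binocular field is one on which reasonable statisticians differ. Nor is it certain that any particular choice is free: if the fields are binocular, an area for the qualifying eye would need a monocular field as well.

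Larger error rates can be produced by supposing six areas, or both eyes entered as independent units. The plan proposes neither, so those rates do not count against it.

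**Conclusion.** The plan leaves the stimulus, the eye and the monocular or binocular mode for the Aim 1 value unstated, and the device state at the return field is only implied. This is a gap that an analyst fills sensibly, with one value per participant in the named comparison and either all isopters shown or III4e used because it defines the patient group. No stated rule or number has been shown to give a wrong result.

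The cost of the gap is modest. For two or three areas the false-positive chance is about 6% to 12% across correlations 0.9 to 0, against 4.3% for one exact test. Disagreement among three areas ranges from 25–53% at 1 SD to 3–5% at 2 SD for correlations 0.9 to 0.5. All of this rests on an assumed two-sided 0.05, ten per group and equally correlated normal changes. In a pilot without a declared significance level, power or success criterion, that does not call for a change.

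### The Aim 2 analysis never uses the device-off walk planned as a negative control, so its before-after comparison cannot separate the display from wearing, practice, training and time

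*Combined protocol and SAP*

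**What the plan says.** **Section a, Study Design (Aim 2).** The aim is to "collect and analyze gait and head movement parameters" in people with severe field constriction and "controls with and without the use of optical head-mounted display technology". At enrolment participants walk an empty corridor, and then "participants will be asked to walk the same corridor after obstacles are arranged in the corridor every 1-2 meters". The walks are done again at the return visit, following a "period of in-home adaptation to the technology with the device turned off (to serve as a negative control) and with the device turned on". That gives three device states (baseline, headset off, headset on) in two corridors, so six walks per participant. The list of return-visit procedures has all mobility testing done with the headset worn. The order of the off and on walks is not stated.

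**Section b, Eligibility.** Healthy controls are enrolled partly so that the headset's own effect on gait can be allowed for. The target is ten patients and ten controls with complete data.

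**Section d, Outcome measures.** The only secondary outcome is "Change in gait speed compared to baseline (measured in seconds"). Stride length, stride width and foot orientation are also defined as changes from baseline. None of these definitions mentions on or off.

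**Section e, Planned Data Analysis (Aim 2).** For gait speed, "we will measure change in gait speed with and without the use of OHMD". Percent preferred walking speed is used to "compare the ratio of gait speed measured in the presence and absence of physical obstacles", with no device state named. For the other parameters, "The mean and standard deviation of each gait and head movement parameter will be compared before and after being trained", with a Wilcoxon signed-rank test. A Mann-Whitney test compares changes in gait parameters between patients and controls.

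**The concern.** The design collects a walk whose declared purpose is to act as a negative control, and the analysis section then gives it no role. Both return-visit walks come after training and home use. A before-versus-after-training comparison is therefore not an on-versus-off comparison, and it does not say which of the two walks is the later value.

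If the later value is the on walk, the result is the net effect of everything that changed between visits: display function, the weight and feel of the headset, having walked the course before, training, and 2-4 weeks' elapsed time. A change could then be credited to the display when the display did nothing. Equally, a headset that slows people down could hide a display that helps them. The walks that would separate these are already being collected.

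**Working it through.** There is no figure in the documents to reproduce. They give no alpha, SD, effect size or practice effect, and the ten per group are not derived from a formula. The check has two parts.

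**1. What each contrast estimates.** Let *w* be the combined non-display shift from baseline to the return visit (wearing, repeat exposure, training, time), *d* the display effect, and *p* any practice gained between the first and second return-visit walk.

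- On minus baseline = *w* + *d*
- Off minus baseline = *w*
- On minus off = *d* + *p* if off is walked first, *d* - *p* if on is walked first
- Patients versus controls, on minus baseline = (*w*<sub>P</sub> - *w*<sub>C</sub>) + (*d*<sub>P</sub> - *d*<sub>C</sub>)

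The first two lines leave *p* aside. The last line shows what the controls achieve. They remove *w* only if it is equal in both groups, and they also remove whatever part of *d* the groups share.

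**2. Illustration of size.** Assumptions, none from the documents: normal errors, SD 1 for every paired difference (including same-day differences, which could well be smaller), two-sided 0.05. The sample size of 10 per group is from section b. With n = 10 the signed-rank test rejects when the smaller rank sum is 8 or less, exact size 0.0488. Rejection rates are simulated.

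| Case | Contrast | Rejects |
|---|---|---|
| *d* = 0, *w* = 0.25 | on minus baseline | about 11% |
| *d* = 0, *w* = 0.5 | on minus baseline | about 28% |
| *d* = 0, *w* = 0.75 | on minus baseline | about 55% |
| *d* = 0, any of these *w*, *p* = 0 | on minus off | about 5% |
| *w* = -1, *d* = +1 | on minus baseline (*w* + *d* = 0) | about 5% |
| *w* = -1, *d* = +1, *p* = 0 | on minus off | about 78% |
| *d* = 0, *w* = 0.5 in both groups | Mann-Whitney, on minus baseline | about 4% |
| *d* = 0, *w* = 0.5 in patients, 0 in controls | Mann-Whitney, on minus baseline | about 16% |

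**Walk order.** With *p* = 0.5 and *d* = 0, the bias of on minus off is 0.5 x (off-first - on-first)/10:

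- 10/0 split: bias 0.5 SD, rejects about 28%
- 7/3 split: bias 0.5 x 4/10 = 0.2 SD, rejects about 6%
- 5/5 split: bias 0, rejects about 3%

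Averaging the two order-specific means gives [(*d* + *p*) + (*d* - *p*)]/2 = *d* whatever the split. A t test on that average (8 df at n = 10) rejects in about 5% at 5/5, 7/3 and 8/2. Its power for *d* = 1.0 is about 79%, 72% and 60% respectively.

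**The case against.** The best defence is that the plan is more settled than it looks. Section d ties gait speed and three other gait outcomes to baseline, the analysis sentence is before and after, and every return-visit walk is done with the headset worn. A reader might infer that 'without' is wholly open and that the secondary outcome has no comparator. The documents do not support that: baseline is the likely comparator. What stays open is which return-visit walk supplies the later value.

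A reader might also infer that the off walk has no purpose at all. That is too strong, because section a states one. What is missing is any outcome or test that carries it out. The stated purpose suggests an on-off comparison was intended, but an intention is not an analysis.

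Nor does the plan ignore non-display effects. The controls are there partly for that reason, and if non-display shifts are equal in the two groups the Mann-Whitney test holds its level (about 4%). But equality is an assumption. Legally blind patients and sighted controls need not respond alike to a worn headset or a repeated obstacle course, and the comparison does not isolate display function within patients.

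Finally, on minus baseline answers a legitimate question, in which training and adaptation are a deliberate part. This stands in full. Under the net-impact question the rejections in the table caused by *w* are not errors.

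**Conclusion.** The point holds in a limited form and should be acted on. The device-off walk has no stated use in the analysis, and the comparison most likely intended cannot attribute a change in mobility to the display. It can err in either direction.

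Confidence is high on the missing on-off contrast, because that rests on the text. The error rates are illustrations that depend on assumed shifts and a common SD; they are not estimates for this trial. It would be wrong to read the 28% as the trial's false-positive rate or to call the before-after test invalid. It is the chance of a misleading result only if on minus baseline is read as display function and the non-display shift happens to be 0.5 SD.

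This is a pilot with ten completers per group. The point affects the interpretation of Aim 2, including the only secondary outcome. It does not touch the primary visual field outcome.

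**What to change.** In section e, state that:

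- (a) the secondary gait-speed outcome is device-on at the return visit minus baseline, the net effect, and 'without' means the baseline walk;
- (b) display function is device-on minus device-off at the return visit, paired within participant (Wilcoxon signed-rank), for gait speed and all gait and head movement parameters, separately for the empty and the obstacle corridor, and for percent preferred walking speed with both of its walks from the same device state;
- (c) device-off minus baseline is reported descriptively as wearing, practice, training and elapsed time combined;
- (d) the patient-control Mann-Whitney test is applied to on minus baseline and, as a supporting analysis, to on minus off.

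In section a, alternate off-first and on-first separately within patients and within controls, assign the order at the return visit so that earlier drop-out cannot unbalance it, and record it. State in advance that, if the order is uneven among completers, the average of the two order-specific means of on minus off (t test, 8 df at n = 10) is also reported.

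**Cost.** No new walks. There are two more sets of paired contrasts, one more between-group test, and a small change in conduct at the return visit. If practice between the two device states is real, a balanced order makes the signed-rank test conservative and costs some power: about 70% instead of 78% for a 1.0 SD display effect with 0.5 SD practice at 5/5. Equipment faults can still unbalance the order, and balancing cancels only practice that is the same size in both orders.
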